Baseline and Study Procedures: After screening, subjects will undergo fMRI and behavioral assessments at baseline followed by stratification by sex and double-blind randomization to either bupropion XL 150mg/d or escitalopram 10mg/d as indicated in Table 1. The randomization scheme will be implemented by research pharmacy, and all patients and study staff will be blinded to treatment assignment. Patients will be randomized in blocks of 4. After 2 weeks, subjects with a HDRS-17_>7_will be increased to bupropion XL 300mg/d or escitalopram 20mg/d as tolerated. fMRI scanning and behavioral assessments will be repeated at 4 and 8 weeks. Vital signs, safety labs, urine toxicology and adverse events will be collected as indicated in Table 1. The primary outcome (Aim 1) will be targeted VS-vmPFC FC as detailed below. Secondary outcomes (Aim 2) will include RDoC positive valence constructs including objective assessments of effort-based decision making and clinician-administered and self-report assessments of motivation/anhedonia (see below). Additional (exploratory) outcomes will include treatment response over time and adverse events.

Table 1. Schedule of Study Procedures and Assessments

	Virtual	Visit 1 Screen	Visit 2		Visit 3	Visit 4	Visit 5	Virtual	Visit 6
Assessments	Intake		Screen B	Base- line A	Base- line B		Wk 4	Wk 6	Wk 8
Consent	Х								
PHQ-9, Medical / Psychiatric Screening***	Х	[X]	[X]						
FERN MRI Screening Form***	[X]	х					Х		Х
ATRQ, Medical History, SCID V-modified (Mood, Anxiety, PTSD modules), Bipolarity index	X								
Laboratory Eval*, Urinalysis, height weight***		Х							
Rapid CRP (Finger Stick)***		Х	Х						
Physical Exam			Х						
Vital Signs		Х	Х		Х	Х	Х		Х
Adverse events**, Concomitant Meds***	Х	Х	Х		Х	Х	Х	х	Х
Urine toxicology screen, pregnancy test***		Х		 	Х		Х		Х
Research bloods†				Х			Х		Х
Neurocognitive Battery				Х		Х	Х		Х
EEfRT (computer-based)				Х	Х	Х	Х		Х
Demographics, habits, CTQ				Х					
MAP, IDS-SR, STAI, BAI, PCL-5, PSS				Х		Х	Х	Х	Х
fMRI					Х		Х		Х
SHAPS-C, CSSRS, CGI					х	Х	Х	Х	Х
HAM-A [Baseline only]****, HAM-D-17					Х	Х	Х		Х
Randomization to bupropion / escitalopram					х				

PI: [name] Sponsor: NIMH

Medication dispensing /compliance check§			Х	Х	Х	Х	Х
Adjustment of medication#				Х	Х	Х	
Discharge/discharge planning					Х	Х	Х

^{*} Laboratory evaluation will include the comprehensive metabolic panel, thyroid-stimulating hormone (TSH), CBC with diff, and plasma CRP.

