The MGH Antidepressant Treatment Response Questionnaire (ATRQ):⁴³ The ATRQ provides specific criteria for adequate dose and adequate length of a trial for it to be considered a failure, thus allowing clinicians to systematically collect data aimed at assessing degree of treatment-resistance of the MD episode. The data obtained can then be used to calculate a score using the MGH Staging Method (MGH-S) to classify degree of treatment resistance.⁴⁰ Degree of resistance will be used as a covariate in relevant statistical analyses and to exclude severely treatment resistant subjects.⁴⁴ Severity of clinical condition and improvement in overall clinical state over the study period will be evaluated at each assessment with the Clinical Global Impressions Scale (CGI)⁴⁵. Inventory of Depressive Symptoms-Self Report (IDS-SR) is a 30-item self-report instrument with excellent psychometric properties that was designed to measure symptom constructs including psychomotor retardation, fatigue and anhedonia consistent with current DSM nosology. MRI neuroimaging: Scans will be carried out in Emory's Facility for Education and Research in Neuroscience (FERN) on a Siemens Trim Trio 3T scanner and 32-channel head coil using the following protocols. Anatomic images: High-resolution T1 weighted images ⁴⁶ will be obtained for co-registration with fMRI data. A localizer scan will be used to orient the 3D volume scan.

^{**} Adverse events will be recorded at each visit after study enrollment (Baseline A until Week 8).

[§] Compliance check will be conducted starting at Week 2 until Week 8.

[#]Medication dosage will be adjusted upward to 2 pills at Week 2 or Week 4 as needed based on tolerability. []To be completed if needed

^{***}These assessments may be conducted at the Emory Behavioral Immunology program research screening clinic

^{****}HAM-A instrument removed from Baseline visit on 7/5/22.

PI: [name] Sponsor: NIMH

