
Targeted FC will serve as the primary outcome and will be calculated as the degree of correlation in activity between a 3mm3 radius sphere in VS (see Fig. 1A)^{25, 62} and the vmPFC cluster identified as being reward-sensitive in neuroimaging meta-analyses⁶³ and as used to define vmPFC in our previous work (MNI coordinates x=0, y=44, z=-8, cluster size=1408 mm3 and encompassing parts of BA11 and ventral BA32 of ACC). 25, 62, 64 This method will ensure rigor and reproducibility and application of results to potential future trials because the seeds and ROI cluster are predefined as opposed to those derived from whole-brain and data-driven analyses which are determined based on the specific patient sample. Zscores will be extracted and the change in mean FC values compared to baseline will be calculated. FC between bilateral VS seeds and the vmPFC ROI will be examined separately and treatment-driven change in FC in either the right or left VS will be considered in the analysis. However, based on our previous work in MD and IFN-alpha-induced depression ^{13, 25} and preliminary studies above, we anticipate that changes in FC will be more pronounced on the left side. Additional Analyses for Publication and Dissemination: In addition to the targeted FC that will serve as the primary outcome, hypothesis-driven and data-driven whole-brain analysis will also be explored and compared before and after L-DOPA and placebo. Consistent with our previously published data,65 these analyses will include VS seed-to-voxelwise comparisons of bupropion versus escitalopram, as well as network analyses using GBC and PBNA, as a secondary outcome measure and to identify other circuits that may be differentially affected by the two treatments. For all analyses, concentration of CRP and final dose will be explored as linear predictors of response.

Assessments of Positive Valence (Motivational) Constructs

Objective: Effort-Expenditure for Rewards Task (EEfRT): The EEfRT task is a multi-trial game in which participants are given an opportunity to choose different task difficulty levels to obtain monetary rewards. The task is 20 min, and first 50 trials are analyzed. The proportion of hard-task choices across each level of probability is calculated. Lower proportions of hard task choices indicate decreased motivation.

PI: [name] Sponsor: NIMH

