Aim 1: To determine whether bupropion (vs escitalopram) will increase FC in reward circuitry. Hypothesis 1: Bupropion vs escitalopram will increase VS-vmPFC FC in depressed patients with high CRP and anhedonia at baseline. Primary Endpoint: Targeted VS-vmPFC FC at 8 weeks. Predictors: group (bupropion vs escitalopram), time (baseline, 8 weeks), and group x time interactions. Covariates: Primary: Age, sex, BMI, race. Additional covariates: Number of depressive episodes, length of current depressive episode (in months), treatment trials (ATRQ), age of onset, and family history of depression (ves/no), weeks on targeted dose of medication, Analysis Plan: Subjects will be randomized to two different treatment groups and scanned across two visits. Consequently, a factorial mixed-effects models for repeated measures (MMRM) will be employed with group, time and group x time interaction on targeted VS-vmPFC FC as fixed effects and each subject's baseline (identity) as random effects. Linear and multi-level mixed effects will be evaluated using both unstructured and autoregressive covariance structures and restricted maximum likelihood estimation and will be used to predict random effects (slope and intercept) in addition to fixed effects, optimized using Bayesian Information Criteria (BIC). Primary and additional covariates will be entered in all models as random variables after testing for significant associations. Given the inherently noisy nature of the covariates, model tuning to optimize the balance between explanatory (r²) and noise variables (root mean square error) will be undertaken to select the most parsimonious models using BIC. The MMRM will also be augmented using Elastic net generalized regression models using group||time nesting approaches. Models will be selected using model comparison metrics. All analyses will be conducted in accordance with published guidelines.⁷⁶ Exploratory analysis: A similar analysis as indicated above will be conducted on fMRI scans conducted at 4 weeks. The 4-week scan will be conducted based on the rapid effects seen with dopamine agonists in our preliminary studies with L-dopa (data not shown).

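### Weeks on targeted dose is determined after randomisation, so adjusting the between-arm models for it can bias the treatment comparison

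*Combined protocol and SAP*

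**What the plan says.** Section 10, Aim 1, names four primary covariates (age, sex, BMI, race) and a longer additional list. That list is mostly history fixed before randomisation, such as number of episodes and age of onset, but it ends with "weeks on targeted dose of medication". The entry rule is "Primary and additional covariates will be entered in all models as random variables after testing for significant associations", followed by tuning with BIC and an elastic-net supplement. Hypothesis 2a takes the same predictors and covariates. Aim 3 takes the relevant ones from Aim 1.

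Dose is settled during treatment:

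- Section 5 (Baseline and Study Procedures) says that patients whose HDRS-17 is above 7 after two weeks are "increased to bupropion XL 300mg/d or escitalopram 20mg/d as tolerated".
- Footnote # to Table 1 says "Medication dosage will be adjusted upward to 2 pills at Week 2 or Week 4 as needed based on tolerability".
- The baseline scan comes before allocation: "subjects will undergo fMRI and behavioral assessments at baseline followed by stratification by sex and double-blind randomization".

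The primary outcome appears in more than one form. Aim 1 gives "Primary Endpoint: Targeted VS-vmPFC FC at 8 weeks" in a model with group, time (baseline, 8 weeks) and group x time. Section 5, on targeted FC, says "the change in mean FC values compared to baseline will be calculated", and Section 11 bases power on that change. Hypothesis 2a controls for baseline score.

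No section confines weeks on targeted dose to a sensitivity or exploratory analysis. Final dose is treated differently: Section 5 says that "concentration of CRP and final dose will be explored as linear predictors of response".

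**The concern.** Randomisation protects the unadjusted comparison and comparisons adjusted for variables fixed before allocation. It does not protect a comparison adjusted for something treatment can change. Weeks on targeted dose (W below) reflects early response and tolerability, and the assigned drug can affect both.

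The problem is plainest in Aim 3. The outcome there is HAM-D-17 from week 2 onward, and the week-2 score on that scale decides who is escalated, so the model would adjust an outcome for a function of its own early value.

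Association testing, BIC and elastic net do not ask whether treatment affects a covariate. They favour W when it tracks the outcome, which is one of the two conditions for bias. Part of a real early effect could be adjusted away, or a tolerability difference could inflate the estimate.

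**Working it through.** **The plan's own figure.** From Section 11, d = (0.20 − 0.07) / √((0.16² + 0.10²)/2) = 0.13 / 0.1334 = 0.97. A two-sided t-test at 0.05 then needs 18 per arm (power 0.81), and 20 per arm gives 0.85. The stated 36 reproduces.

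**Mechanism.** In a change-score model,

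adjusted difference = total difference − b × (mean W on bupropion − mean W on escitalopram),

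where b is the within-arm slope of outcome change on W. The bias is zero if the means are equal or if b = 0.

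**Inputs.** The true effects come from Section 11 (0.97 SD for FC, 1.0 SD for EEfRT). Everything else is assumed, because the documents give no escalation or tolerability rates:

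- W = 6 weeks if the patient is above the week-2 cut-off and tolerates the increase, otherwise 0.
- 8% of escitalopram patients are at or below the cut-off.
- 85% tolerate the increase in both arms.
- Bupropion has an early-response advantage of 0.5 or 1.0 SD, which puts 18% or 34% of its patients at or below the cut-off.
- The within-arm correlation r between week-2 response and outcome change is 0.43 or 0.6. The 0.43 is Section 11's FC-EEfRT correlation, borrowed only as a scale.

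Mean W is 6 × 0.85 × 0.92 = 4.7 weeks on escitalopram. On bupropion it is 6 × 0.85 × 0.82 = 4.2 (0.5 SD) or 6 × 0.85 × 0.66 = 3.4 (1.0 SD).

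**FC, change score regressed on group and W** (simulated, 1,000,000 patients per scenario, true effect 0.97):

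| Early advantage | r = 0.43 | r = 0.6 |
|---|---|---|
| none | 0.97 | 0.97 |
| 0.5 SD | 0.94 | 0.92 |
| 1.0 SD | 0.87 | 0.83 |

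Adjusting for baseline as well gives the same values to within about 0.01.

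**Tolerability difference only** (bupropion vs escitalopram, r = 0.43 and 0.6):

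| Share at or below cut-off, both arms | 70% vs 95% | 95% vs 70% |
|---|---|---|
| 8% | 0.90, 0.87 | 1.04, 1.07 |
| 30% | 0.88, 0.84 | 1.06, 1.10 |

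**Direct effect of dose, r = 0.** With 0.05 SD gained per week on dose, the total effect is 0.97 − 0.05 × (4.69 − 4.17) = 0.94 for the 0.5 SD advantage, or 0.97 − 0.05 × (4.69 − 3.36) = 0.90 for 1.0 SD. The adjusted model returns 0.97 in both cases, so zero shared prognosis does not guarantee zero bias.

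**Two-visit repeated-measures model, complete data** (group x time / week-8 difference):

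| Form of W | 0.5 SD, r = 0.43 | 1.0 SD, r = 0.6 |
|---|---|---|
| not included | 0.97 / 0.97 | 0.97 / 0.97 |
| constant main effect | 0.97 / 0.95 | 0.97 / 0.90 |
| time-varying, 0 at baseline | 0.94 / 0.94 | 0.83 / 0.83 |
| W x time | 0.94 / 0.94 | 0.83 / 0.83 |

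The week-8 shift under a constant main effect assumes roughly equal variances at the two visits.

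**Hypothesis 2a.** A baseline-adjusted random-intercept model with constant W and assumed true differences of 0.5, 0.75 and 1.0 SD at weeks 2, 4 and 8 gives a week-8 difference of 0.86 to 0.97 instead of 1.00. Week 8 minus week 2 stays at 0.50.

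**Chance of entry.** At 20 per arm, in the early-response scenarios, W enters in 24–64% of trials if screened at p < 0.05 without group in the model, 20–45% with group, and 24–50% by BIC. The plan does not state the form of the test.

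**A second set of assumptions** was tried: change SD 0.13, week-2 HDRS mean 14 and SD 5, correlations 0.3 to 0.6, some escalation at week 4, and tolerability that is equal or 90% vs 70%. When W differs by arm, a true FC difference of 0.130 becomes 0.113 to 0.128, which is 2–13% too small. At 0.113, d = 0.113 / 0.1334 = 0.85, and power at 20 per arm falls from 0.85 to about 0.74.

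**The case against.** The strongest reply is that the stated Aim 1 test is group x time, and that W sits in a list of one-value-per-patient items. Entered that way with complete data, it leaves group x time untouched. That is correct as far as it goes. But the plan does not state the coding, W coded by visit is zero at the pre-randomisation scan and therefore time-varying, and 20% attrition is projected. Even with constant coding the week-8 difference moves, and week 8 is the stated endpoint.

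Second, the sizes are assumed, and the larger ones need strong inputs. Nothing in the documents links week-2 response to FC change, and the 0.83 result needs a 1.0 SD advantage by week 2 together with r = 0.6. With a 0.5 SD advantage and r of 0.1 to 0.3, the estimate is about 0.96 to 0.95, and W enters less often. The standard error at 20 per arm is about √(2/20) = 0.32 SD, so even a 0.14 bias is under half of it. This stands as a limit on likely size. It does not make the adjustment valid.

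Third, the term is undefined. If early responders count as on target for all 8 weeks, the early-response range is 0.90 to 0.96. The plan also enters covariates as random variables and adds elastic net, whereas the calculations treat W as an ordinary fixed covariate, which is one reading. Finally, Aim 3 takes only relevant covariates, so its carry-over is less explicit than that of Hypothesis 2a. These points add uncertainty about size and leave the mechanism intact.

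**Conclusion.** The concern holds. A stated covariate rule allows a post-randomisation variable into the between-arm models, and adjusting for it can bias the week-8 FC difference, the change-from-baseline comparison and the baseline-adjusted Hypothesis 2a comparison. Group x time in the two-visit model is protected only with a constant main effect and complete data, and the plan specifies neither.

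In the illustrative scenarios the early-response bias runs from 0.03 to 0.14 SD towards zero in the change-score model. A tolerability difference can push the estimate either way, from 0.84 to 1.10. There is no bias if the arms do not differ in time on the targeted dose, or if that time is unrelated to outcome within arm. Confidence is high that adjustment can bias; how large the bias would be, and in which direction, cannot be settled from the documents. This should be changed before the analysis is fixed.

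**What to change.** - Remove weeks on targeted dose from the covariate list of every between-arm model: Aim 1, Hypothesis 2a and Aim 3.
- State that these models adjust only for variables fixed before randomisation, and always keep sex, since randomisation is stratified by it.
- Report weeks on dose, and the final-dose predictor in Section 5 (also post-randomisation), only in analyses labelled exploratory and kept separate from the between-arm test.
- If dose exposure is reported, define targeted dose, and reconcile Section 5 with footnote # to Table 1 on when the increase occurs.

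The cost is a change of wording. No new data are needed, and the figures of 36, 40 and 50 patients stand. Any precision this covariate would have added is given up.

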The overall objective of the proposed research is to determine the mechanism of action of an antidepressant of known efficacy and tie this mechanism of action to a specific biomarker, ultimately supporting precision medicine in the treatment of major depression (MD). More specifically, the proposed research is designed to determine whether bupropion (vs escitalopram) increases functional connectivity (FC) within reward-related neurocircuits and decreases motivational deficits in depressed patients with increased inflammation and anhedonia. Work by our group and others has demonstrated that administration of inflammatory stimuli to humans is associated with significant decreases in neural activity in the ventral striatum in association with symptoms of anhedonia. In studies in laboratory animals and humans, these effects of inflammation appear to be secondary to decreased dopamine (DA) neurotransmission. Data also indicate that MD patients with higher inflammation as indexed by C-reactive protein (CRP) exhibit lower FC between the DA-rich ventral striatum and ventromedial prefrontal cortex in association with motivational deficits and anhedonia that can be reversed by a DAergic drug (L-DOPA). Further relevant to the proposed research, in a recent clinical trial, depressed patients with increased inflammation (CRP≥1mg/L) showed a poor response to the selective serotonin reuptake inhibitor (SSRI) escitalopram alone, while treatment response was markedly increased in escitalopram-treated patients with the addition of bupropion. Bupropion is a DA reuptake inhibitor that exhibits ~25% occupancy of the DA transporter at therapeutic doses and increases DA neurotransmission in animal models. Taken together, these data suggest that inflammation affects DAergic pathways to disrupt reward-related circuits in depressed patients, leading to motivational deficits. Moreover, in the context of inflammation, drugs that target DA may be more efficacious than SSRIs. Thus, the current study proposes to use a mechanistic clinical trial design with drugs of known efficacy to take the first step toward establishing whether antidepressants that target DA (e.g. bupropion) might be a better choice for depressed patients with increased inflammation and anhedonia than an SSRI. Accordingly, 50 depressed patients with a CRP>2mg/L and increased anhedonia will be randomized to 8 weeks of bupropion or escitalopram in order to analyze data from 40 patients (accounting for drop outs). All depressed patients will undergo functional magnetic resonance imaging (fMRI) to examine FC in reward-related circuits at baseline, 4 and 8 weeks along with objective and clinical assessments of RDoC positive (motivational) valence constructs at baseline and 2, 4, 6 and 8 weeks. We hypothesize that patients who receive bupropion versus escitalopram will exhibit increased FC between ventral striatum and ventromedial prefrontal cortex in association with decreased motivational deficits and anhedonia. This pilot study will provide foundational data for design of larger mechanistic clinical trials that will establish the mechanism of action of conventional antidepressants and determine whether biomarkers of inflammation can be used to facilitate antidepressant choice, increase antidepressant efficacy and ultimately personalize antidepressant treatment.

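### The primary FC model asks for random intercepts and slopes that two scans cannot identify, and separately leaves the scheduled week-4 scan out, so patients who leave after week 4 contribute no FC change

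*Combined protocol and SAP*

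**What the plan says.** Section 10, Aim 1, names targeted VS-vmPFC FC at 8 weeks as the primary endpoint and lists the time factor as "time (baseline, 8 weeks), and group x time interactions". The analysis plan starts from the premise "Subjects will be randomized to two different treatment groups and scanned across two visits" and derives a mixed model for repeated measures from it.

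The random structure is then described twice. One sentence gives "each subject's baseline (identity) as random effects", which reads as a subject intercept. The next says that models will be evaluated "using both unstructured and autoregressive covariance structures and restricted maximum likelihood estimation" and that they "will be used to predict random effects (slope and intercept) in addition to fixed effects". Selection is by BIC.

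Section 5, Baseline and Study Procedures, schedules three scans: after the baseline scan, "fMRI scanning and behavioral assessments will be repeated at 4 and 8 weeks". Section 4 and Table 1 agree. Week 4 enters section 10 only as an exploratory item: "A similar analysis as indicated above will be conducted on fMRI scans conducted at 4 weeks". Section 5 projects 20% attrition (50 randomised, 40 complete), and section 10 gives no missing-data method for FC.

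**The concern.** There are two separate problems.

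The first is that the random effects requested for the primary endpoint cannot be recovered from two observations per patient. Something must be dropped before the model is well defined. The plan's two descriptions of the random structure do not agree on what remains, so the primary model is not fixed in advance. Any predicted individual slopes would reflect how the software splits the variance rather than the data. The exploratory week-4 analysis has the same defect if it uses baseline and week 4 only.

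The second is that the count of two visits conflicts with the three scheduled scans, and the primary model is built on the wrong count. A patient who has the week-4 scan and then leaves has an observed FC change that the primary model does not use. If leaving is related to that change, and differently so by arm, the week-8 comparison is biased when it need not be.

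**Working it through.** **Inputs from the documents.** FC change 0.20 (SD 0.16) for bupropion and 0.07 (SD 0.10) for escitalopram, both proxies from preliminary data (section 11). 50 randomised and 40 complete (section 5), taken as 25 per arm with 5 dropouts each. Scans at weeks 0, 4 and 8 (section 5, Table 1); primary model on weeks 0 and 8 (section 10).

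**Assumed, not in the documents.** Within-patient correlation, timing of dropout and its relation to FC, two-sided testing.

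**1. The plan's own figure.** d = (0.20 - 0.07) / sqrt((0.16² + 0.10²)/2) = 0.13/0.1334 = 0.974. At d = 0.97 and two-sided alpha 0.05, the noncentral t gives power 0.783 with 17 per group, 0.807 with 18 and 0.848 with 20. The stated 18 per group is reproduced, and this point does not alter it.

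**2. Identification with two scans.** Let a be the intercept variance, b the slope variance per week, c their covariance and s the residual variance.

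- Var(week 0) = a + s
- Cov(week 0, week 8) = a + 8c
- Var(week 8) = a + 16c + 64b + s

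That is three equations in four unknowns. Raise s by δ, lower a by δ, raise c by δ/8 and lower b by δ/32. The first two lines do not change, and the third changes by -δ + 2δ - 2δ + δ = 0.

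As an illustration, take variances 0.020 and 0.022 and covariance 0.010. Then b = (0.020 + 0.022 - 0.020 - 2s)/64 = (0.022 - 2s)/64. Residual variances of 0.0005, 0.003, 0.006 and 0.009 give slope variances of 0.000328, 0.000250, 0.000156 and 0.000062. In a simulated data set all four had the same log-likelihood, 57.7133.

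Parameter counts against the rank of the map to the covariance matrix, for random intercept plus slope:

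| Residual structure | Two scans (3 elements) | Three scans (6 elements) |
|---|---|---|
| Independent | 4 parameters, rank 3 | 4 parameters, rank 4 |
| AR(1) | 5 parameters, rank 3 | 5 parameters, rank 5 |
| Unstructured | 6 parameters, rank 3 | 9 parameters, rank 6 |

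On two scans, a random intercept with independent residuals is identified (2 parameters, rank 2). A random intercept combined with AR(1) (3 parameters, rank 2) or with an unstructured residual (4 parameters, rank 3) is not.

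**3. The fixed contrast.** With complete two-scan data the group x time estimate is the difference in mean change. Its standard error depends on Var(week 8 - week 0) = 64b + 2s, which equals 0.022 in every row of the illustration. The contrast therefore does not depend on how the variance is split.

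**4. What week 4 adds in precision.** Generalised least squares, 20 complete and 5 without week 8 per arm, compound symmetry with correlation 0.3, 0.5 and 0.7. The variance of the week-8 contrast with week 4, relative to without it, is 0.996, 0.990 and 0.983 if half the dropouts have a week-4 scan, 0.993, 0.982 and 0.970 if all do, and 1 if none do. Across all settings examined the gain is 0-4%.

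**5. What week 4 adds against bias.** Scenario: 5 dropouts per arm, those on escitalopram mainly the patients with the poorest week-4 FC change, those on bupropion random, correlation 0.4-0.7. The week-8 mean in each arm is estimated given baseline (two scans) or given baseline and week 4 (three scans), keeping all randomised patients.

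- True d: 0.97
- Two-scan model: about 0.86-0.96
- Three-scan model: about 0.97-0.99

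If the same mechanism acts in both arms, the bias is small. A large-sample calculation with dropout depending on week-4 change gave two-scan differences of 0.1287, 0.1279 and 0.1265 at correlations 0.3, 0.5 and 0.7. Divided by 0.1334 these are d of 0.965, 0.959 and 0.948. Across the settings tried the bias stayed within about 0.05 of d.

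**The case against.** Several stronger readings are tempting, and the documents do not support them.

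- **That the primary analysis will not run.** A random intercept and slope model fitted by REML to simulated two-scan data (20 per arm) converged. Its interaction (0.578, SE 0.309) matched a random-intercept fit and a t-test on change scores. Some software may refuse the model, but the test is under-specified rather than impossible.
- **That choosing a covariance structure by BIC is empty on two scans.** Unstructured has three parameters and AR(1) has two, so BIC compares unequal with equal variances. That is a real comparison. BIC may also discard the redundant slope, so simplification is foreseen, but it is then made on the trial data.
- **That identification requires week 4.** Dropping the random effects cures it on two scans, and adding week 4 does not identify random slopes combined with an unstructured residual. The case for week 4 rests on dropout alone.
- **That the plan analyses completers only.** A larger bias can be shown against completers, but section 10 specifies a likelihood-based mixed model and does not restrict it to them. The 40 is a recruitment target. The fair comparator is a two-scan model that keeps dropouts' baselines.

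It is also fair to say that making week 8 primary and week 4 exploratory is a legitimate choice, that week 4 is not ignored (it has its own analysis and enters the interim rule), and that none of the listed discontinuation reasons is FC itself. Week 4's ability to correct the bias follows partly from assuming that loss depends on the observed week-4 FC. What stands is that the random structure is unidentified as written, that the visit count contradicts the schedule, and that information on late dropouts goes unused.

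**Conclusion.** The point holds in two limited parts.

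That the random intercept and slope components are not identified on two scans is a matter of algebra and needs no assumption. Its consequence is that the primary model is not fully pre-specified. It does not invalidate the group x time test.

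The dropout part is conditional. The loss is roughly 0.01-0.11 of d (0.97 less 0.96, to 0.97 less 0.86) if FC-related dropout is concentrated in the escitalopram arm, and within about 0.05 if both arms behave alike. There is no benefit for patients who leave before week 4. The correlation, dropout pattern and timing are assumed. The discontinuation rule for a 25% rise in HAM-D-17 makes loss related to response plausible, but its link to FC is not documented. Precision is not a reason for the change. The correction is worth making before unblinding because it concerns the primary endpoint and needs no new data.

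**What to change.** In section 10, Aim 1:

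- Drop the random effects. Specify one REML model for all randomised patients with any scan, with baseline, week 4 and week 8 FC as outcomes, categorical time, group x time and one unstructured within-patient covariance. Three scans supply exactly the six covariance elements that it needs.
- Keep the week-8 between-group contrast in FC change as the primary test, and read the week-4 contrast from the same fit as exploratory.
- Reconcile this with the Interim Analysis rule, under which the trial may continue with its focus on whichever scan shows the larger effect. State which contrast is then primary.
- Correct the count of two scanning visits to three.

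The cost is wording and three more covariance parameters (six instead of three), which is a modest burden with about 50 patients. No additional scans are needed.
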